#### **10.7.3. Weeks 2, 3, 5, and 6 (and additional RT weeks if needed)**

Prior to RT administration, the following observations and procedures will be conducted for all subjects on all RT days:

- Record concomitant medications and need for parenteral or tube feeding
- Record AEs
- Conduct esophagitis assessment daily and record the severity using both the CTCAE and RTOG grading scales.
- Ensure the daily swallowing diary is completed.

Prior to GC4419 administration, the following observations and procedures will be conducted for all subjects once each week:

- Record analgesic / narcotic use
- Have the patient complete the PROs and NPRS and review completion.
- Draw blood for laboratory measurements:
  - Chemistry profile
  - Hematology profile

Administer GC4419 doses by continuous IV infusion. GC4419 should be administered so that RT is administered within 60 minutes of the end of the GC4419 infusion.

#### **10.7.4. Week 4**

Prior to RT administration, the following observations and procedures will be conducted for all subjects on **all RT days**:

- Record concomitant medications and need for parenteral or tube feeding
- Record AEs
- Conduct esophagitis assessment daily and record the severity using both the CTCAE and RTOG grading scales.
- Ensure the daily swallowing diary is completed.

Prior to GC4419 administration, the following observations and procedures will be conducted for all subjects **once this week**:

- Record analgesic / narcotic use
- Perform symptom-directed PE
- Have the patient complete the PROs and NPRS and review completion.
- Measure vital signs, body weight and ECOG Performance Status
- Draw blood for laboratory measurements:
  - Chemistry profile
  - Hematology profile
  - PK sampling (See [Section 10.3](#)) – Day 22 only

Administer GC4419 doses by continuous IV infusion. GC4419 should be administered so that RT is administered within 60 minutes of the end of the GC4419 infusion.

#### **10.7.5. Last Day of RT or Early Termination Visit**

Prior to RT administration, the following observations and procedures will be conducted for all subjects on the last day of RT or if the patient terminates study participation early:

- Conduct a complete physical examination
- Measure vital signs, body weight, and ECOG status
- Pneumonitis Assessment: NCI-CTCAE scale, CT scan, spirometry, and DLCO
- Ensure the daily swallowing diary is completed
- Conduct Esophagitis assessment for the week and record the severity using both the CTCAE and RTOG scales
- Have the patient complete the PROs and NPRS and review completion
- Record any concomitant medications including analgesic/narcotic use and need for parenteral or tube feeding
- Record AEs
- Draw blood for laboratory measurements:
  - Chemistry profile
  - Hematology profile

#### **10.7.6. 4 Weeks Post-RT**

All subjects will be evaluated at  $28 \pm 15$  calendar days from the last day of RT. The following should be completed at this visit:

- Conduct a complete physical examination
- Measure vital signs, body weight, and ECOG status

- Record any concomitant medications including analgesic/narcotic use and need for parenteral or tube feeding
- Record AEs through 30 days after the last dose of RT
- Conduct Esophagitis assessment for the week and record the severity using both the CTCAE and RTOG scales
- Have the patient complete the PROs and NPRS review completion.
- Collect swallowing diary and ensure it was completed daily through 4 Weeks post-RT
- Draw blood for laboratory measurements:
  - Chemistry profile
  - Hematology profile

## **10.8 Post Active Phase**

### **10.8.1 90 Days Post-RT**

All subjects will be evaluated at  $90 \pm 15$  calendar days from the last day of RT. The following should be completed at this visit.

- Conduct a complete physical examination
- Pneumonitis Assessment: CT scan, spirometry, and DLCO. Evaluate for acute RT pneumonitis,  $\geq$  Grade 2 by the NCI-CTCAE scale
- Record any updates to SAEs which were ongoing at the 4 weeks post-RT visit
- Tumor Assessment: Chest CT (with or without contrast) to be performed based on standard of care CT follow up

### **10.8.2 6 months, 9 months and 1-year post-RT ( $\pm 30$ days)**

Subjects will undergo a physical exam and Chest CT (with or without contrast) based on standard of care CT follow-up

## 11. ADVERSE EVENTS AND SERIOUS ADVERSE EVENTS

The investigator is responsible for the detection and documentation of events meeting the criteria and definition of an AE or SAE as provided in this protocol. Throughout the study, AEs will be recorded in the source documents and on the appropriate pages of the CRF regardless of whether the AEs are considered related to GC4419. To avoid confusion, the AE should be recorded in standard medical terminology.

### 11.1. Definitions

The following definitions of terms are guided by the International Conference on Harmonization and the US Code of Federal Regulations and are included here verbatim.

#### 11.1.1. Adverse Event (AE)

An AE is any untoward medical occurrence in a patient or clinical investigation subject administered a pharmaceutical product and which does not necessarily have a causal relationship with this treatment. An AE can therefore be any unfavorable and unintended sign (including an abnormal laboratory finding), symptom, or disease temporally associated with the use of a medicinal (investigational) product, whether related to the medicinal (investigational) product.

**Examples of an AE include:**

- Significant or unexpected worsening or exacerbation of the condition/indication under study.
- Exacerbation of a chronic or intermittent pre-existing condition including either an increase in frequency and/or intensity (grade) of the condition.
- New conditions detected or diagnosed after investigational product administration even though they may have been present prior to the start of the study.
- Signs, symptoms, or the clinical sequelae associated with a suspected interaction of the investigational product with a concomitant medication.
- Signs, symptoms, or the clinical sequelae associated with a suspected overdose of either investigational product or a concurrent medication.

#### 11.1.2. Serious Adverse Event (SAE)

Any untoward medical occurrence that at any dose:

- Results in death,
- Is life-threatening – *NOTE: The term 'life-threatening' in the definition of 'serious' refers to any adverse drug experience [adverse event] that places the patient or subject, in the view of the investigator, at immediate risk of death from the reaction as it occurred, ie, it does not include a reaction that, had it occurred in a more severe form, might have caused death. [emphasis added]*
- Requires inpatient hospitalization or prolongation of hospitalization – *NOTE: In general, hospitalization signifies that the patient or subject has been detained (usually involving at least an overnight stay) at the hospital or emergency ward for observation and/or*

*treatment that would not have been appropriate in the physician's office or outpatient setting. Complications that occur during hospitalization are AEs. If a complication prolongs hospitalization or fulfills any other serious criteria, the event is serious. When in doubt as to whether "hospitalization" occurred or was necessary, the AE should be considered serious. Hospitalization for elective treatment of a pre-existing condition that did not worsen from baseline is not considered an AE.*

- Results in persistent or significant disability/incapacity – *NOTE: The term disability means a substantial disruption of a person's ability to conduct normal life functions.*

OR

- Is a congenital abnormality/birth defect.
- Is a other important medical event

## **11.2. Adverse Event Reporting Requirements**

### **11.2.1. Serious Adverse Events**

All events meeting the criteria for SAEs (see [Section 11.1.2](#)) must be reported by investigational sites within 24-hours of becoming aware of the event. In order to determine the sponsor's timeline for notifying regulatory authorities and investigators per Federal Regulations, an event term, serious criteria, and causality is required at the time of the initial report. Specific SAE reporting instructions are provided in a separate manual.

The investigator is responsible for notifying the IRB/IEC/REB in writing of serious events as soon as is practical in accordance with the policy of the IRB/IEC/REB.

### **11.2.2. All Adverse Events (AEs) Regardless of Seriousness**

Any adverse medical condition or laboratory abnormality with an onset date before the date of the baseline visit is pre-existing in nature, and part of a subject's medical history. Adverse medical conditions that begin on or after date of baseline visit will be considered an AE, including SAEs, and followed for 30 days after the last dose of RT, chemotherapy, or GC4419 (ie, whichever occurs last), hereafter referred to as the "30 Day Follow-up Period". Similarly, new events will be reported as AEs/SAEs if the start date is within 30 Day Follow-up Period. Increases in toxicity grade of pre-existing conditions that occur on or after the date of the baseline visit are also considered an AE.

All AEs must be recorded in the patient's source documents and on the CRF regardless of frequency, severity (grade) or assessed relationship to study drug.

### **11.2.3. Clinical Laboratory Abnormalities and Other Abnormal Assessments as AEs and SAEs**

Clinically significant abnormal laboratory findings or other abnormal assessments that are associated with the disease being studied, unless judged by the investigator as more severe than expected for the patient's condition, or that are present or detected at the time of the baseline visit and do not worsen, will not be reported as AEs or SAEs.

A laboratory abnormality reported by either the central laboratory or local laboratory may meet the criteria to qualify as an AE or SAE as described in this protocol. Laboratory abnormalities should only be recorded in the AE section of the CRF if at least one of the following criteria is met:

- Meets the criteria of an SAE
- Resulted in a dose reduction and/or delay in the administration of GC4419, RT, and/or chemotherapy
- Treatment is initiated for the abnormality
- Investigational product was discontinued
- Grade 3 or Grade 4 per (NCI-CTCAE version 5.0)

For laboratory abnormalities meeting the criteria of SAEs, the site must complete and send the SAE report including the laboratory report (as regionally required) to the sponsor using the SAE form. Abnormal assessments (eg, ECGs) that are judged by the investigator as clinically significant will be recorded as AEs or SAEs if they meet the definitions as defined in [Section 11.1](#).

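### Section 11.2.3 exempts disease-associated findings from SAE reporting with no exception for those that meet SAE criteria, which conflicts with the SAE duty in Sections 10.1.2, 11.2.1 and 11.2.3 itself

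*Combined protocol and SAP*

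**What the plan says.** Four places in the protocol bear on this.

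- **Section 11.2.3, first paragraph.** It takes "Clinically significant abnormal laboratory findings or other abnormal assessments that are associated with the disease being studied" and says that they "will not be reported as AEs or SAEs". The exemption is lifted for a finding "unless judged by the investigator as more severe than expected" for that patient. A separate limb exempts findings already present at the baseline visit that do not worsen. Neither seriousness nor grade is mentioned as an exception.
- **Section 11.2.3, second and third paragraphs.** "Laboratory abnormalities should only be recorded in the AE section of the CRF if at least one of the following criteria is met". The five criteria include "Meets the criteria of an SAE" and "Grade 3 or Grade 4 per (NCI-CTCAE version 5.0"); the other three are a reduced or delayed treatment, treatment started for the abnormality, and discontinuation of the investigational product. The section then obliges the site to send an SAE report for any laboratory abnormality meeting SAE criteria. It also says that clinically significant abnormal assessments are recorded if they meet the Section 11.1 definitions.
- **Section 10.1.2.** It repeats the obligation to send an SAE report for a laboratory abnormality that meets SAE criteria. It also says that local laboratory results are not collected.
- **Sections 11.2.1 and 11.2.2.** All events meeting SAE criteria "must be reported by investigational sites within 24-hours of becoming aware of the event". All AEs are recorded "on the CRF regardless of frequency, severity (grade) or assessed relationship to study drug".

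**The concern.** The exemption turns on two investigator judgments: that the finding goes with the disease, and that it is no worse than expected. The SAE criteria in Section 11.1.2 are mainly about outcome: death, threat to life, hospitalization, disability. These are different questions. A finding can be expected in a patient with lung cancer and still meet an SAE criterion. For such a finding one sentence tells the site not to report, and three other places tell it to report.

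The order of steps also matters. Section 11.3 allows an event to be called unrelated to GC4419 only with a high level of certainty and a clear precipitating cause. Section 11.8 leaves the final decision on reportability to the sponsor. The exemption applies a looser test, association with the disease, before either step is reached. If a site follows it, the sponsor never sees the event.

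The wording is also open. Section 11.2.4, whose heading speaks of disease-related events, covers both esophagitis and progressive disease. A site could therefore take the disease being studied to be esophagitis, and so treat laboratory consequences of poor intake as exempt.

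At stake are the AE/SAE incidence tables in a single-arm trial, expedited reporting, and local-laboratory abnormalities, which reach the database only through an AE or SAE record.

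**Working it through.** No arithmetic applies: the point depends on no rate, sample size or error level, and the plan states no figure for it. The check is to take each kind of finding and read the rules side by side.

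1. **Disease-associated, more severe than expected.** The clause in 11.2.3 lifts the exemption. All rules point to reporting, and this agrees with the example in Section 11.1.1 that treats significant or unexpected worsening of the condition under study as an AE. No conflict.
2. **Disease-associated, as expected, meeting SAE criteria.** The first paragraph of 11.2.3 says not to report as an AE or SAE. Its third paragraph and Section 10.1.2 say a laboratory abnormality of this kind must be sent as an SAE report, and 11.2.1 adds the 24-hour limit for all SAEs. None of these excepts disease-associated findings, and nothing says which rule prevails. Conflict.
3. **Disease-associated, as expected, Grade 3-4 or meeting another listed criterion, not serious.** The list is introduced with the words only and if. Read literally, it sets a necessary condition for recording. A filter of that kind can stand beside the exemption: the finding passes the filter and is still exempt. If the list is read as an instruction to record, the two rules collide. The text does not settle which reading is meant. Ambiguity.
4. **Caused by chemotherapy, radiotherapy or GC4419.** The disease-association limb does not reach it if the disease is lung cancer. No conflict on that reading. If the disease is read as esophagitis, some findings of this kind could be drawn in.
5. **Present at baseline and not worsening.** This is exempt under the second limb, and it is consistent with 11.2.2, which treats abnormalities with onset before baseline as medical history. No conflict, and this limb should be left alone.

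Section 11.2.2 adds little to case 2 or 3. It governs events that are AEs, while 11.2.3 decides which findings are reported as AEs at all.

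**What would be lost.** Section 12.5 summarizes laboratory measurements at the protocol time points separately from the AE tables. Appendix 1 schedules central laboratory tests at screening, twice in Week 1, then weekly through the end of radiotherapy, and at the 4-week visit. Those values stay in the data whatever is done with the AE form. What can be lost is the AE or SAE record, the expedited report that depends on it, and any abnormality measured only locally.

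**The case against.** The strongest reply is that the duty to report serious findings is written several times, in mandatory terms and without exception, so a careful site would report. A hospitalization or a life-threatening clinical event is not a laboratory finding or an assessment and stays reportable under 11.2.1. Section 11.4 also prefers a diagnosis to a symptom and asks for symptomatic progression to be recorded. Section 11.2.1 further refers to a separate manual of SAE instructions, which may resolve the matter. This narrows the conflict to a finding that itself meets SAE criteria. It does not remove it, because the exemption names SAEs expressly and the protocol gives no rule of precedence.

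A reader might infer four stronger things that the documents do not support.

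- **That the section expressly exempts serious or Grade 3-4 findings.** It does not say so. For serious findings the conflict comes from a missing exception, and the clause on greater-than-expected severity limits it. For Grade 3-4 there is only the ambiguity in case 3.
- **That these events vanish from the safety data, or that the AE tables are the only account of safety.** Section 10.1 bases safety on examination, laboratory tests, ECG and vital signs as well, and Section 12.5 summarizes the laboratory, vital-sign and ECG data.
- **That lung CT, spirometry and DLCO results are hidden.** They belong to a separately scheduled pneumonitis assessment, and pneumonitis of Grade 2 or higher is a secondary endpoint.
- **That sites are shown to report differently.** Without the SAE manual this cannot be shown; the protocol text alone permits it.

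**Conclusion.** The point holds in a narrow form. Section 11.2.3 exempts disease-associated findings that are no more severe than expected from SAE reporting. It makes no exception for those that meet SAE criteria, so it cannot be squared with its own third paragraph, with 10.1.2 or with 11.2.1. Its interaction with the remaining recording criteria is unclear. This is a drafting inconsistency in a safety-reporting rule. It does not touch treatment or the primary analysis.

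Its size cannot be estimated. The documents give no expected rate of such findings and no basis for guessing how many would be withheld, so any assumed count among the approximately 60 planned subjects would be invented. The conclusion rests on the protocol text alone, and on the assumption that the separate SAE manual does not already set the precedence.

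**What to change.** Amend the first paragraph of Section 11.2.3 in four respects.

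1. State that the disease-association exemption does not apply to any finding meeting Section 11.1.2, and that such a finding is reported within 24 hours whatever its presumed cause.
2. Say whether a disease-associated laboratory abnormality that meets one of the other four listed criteria, including Grade 3-4, is recorded as an AE.
3. Replace the reference to the disease being studied with the underlying lung cancer, so that esophagitis is not read into it.
4. Keep the separate exemption for baseline findings that do not worsen. A blanket rule that any abnormality meeting a listed criterion is recorded would turn a stable baseline Grade 3 value into an AE and clash with 11.2.2.

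Check that the SAE manual says the same. The cost is one amended paragraph and a few more AE/SAE forms.

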#### **11.2.4. Disease-related Events and/or Disease-related Outcomes Not Qualifying as SAEs**

Esophagitis will not be reported as AEs as it is captured as a study endpoint in the CRF. Progressive disease found by scan or on clinical evaluation should be captured on the applicable CRF pages and not as an AE.

#### **11.2.5. Grading of Adverse Events**

The severity of AEs will be designated as mild, moderate, severe, life threatening, or fatal per NCI-CTCAE version 5.0. If not specifically addressed in NCI-CTCAE version 5.0, use Table 4 below:

**Table 4. Adverse Event Severity**

Grade	Criteria 
Mild – Grade 1	Asymptomatic or mild symptoms; clinical or diagnostic observations only; intervention not indicated
Moderate – Grade 2	Minimal, local, or non-invasive intervention indicated; limiting age-appropriate instrumental ADL 
Severe – Grade 3	Severe or medically significant but not immediately life-threatening; hospitalization or prolongation of hospitalization indicated; disabling; limiting self-care ADL 
Life Threatening – Grade 4	Life-threatening consequences; urgent intervention indicated
Death – Grade 5	Death related to adverse event

ADL = Activities of Daily Living.

 A semi-colon indicates ‘or’ within the description of the grade.

 Instrumental ADL refer to preparing meals, shopping for groceries or clothes, using the telephone, managing money, etc.

 Self-care ADL refer to bathing, dressing and undressing, feeding self, using the toilet, taking medications, and not bedridden.

### 11.3. Relationship to Study Drug

All AEs will be categorized by the investigator with respect to their relationship to GC4419. The relationship between GC4419 and the AE may be considered related, possibly related, or unrelated. The criteria for each category are listed below:

- **Related:** It is likely that GC4419 caused or contributed to the cause of the AE or laboratory abnormality, when the temporal sequence from the time of GC4419 administration, the known consequences of the patient’s clinical/state condition or study procedures, the effects of discontinuing or re-introducing GC4419 on the AE, and other medically relevant factors are considered.
- **Possibly Related:** There is a reasonable possibility that the AE or laboratory abnormality was caused by GC4419, when the temporal sequence from the time of GC4419 administration, the known consequences of the patient’s clinical state/condition or study procedures, and other medically relevant factors are considered.
- **Unrelated:** The investigator has a high level of certainty that the patient’s clinical state/condition, study procedures, or other medically relevant factors other than treatment with GC4419 caused the AE or laboratory abnormality. This relationship category should only be used when a clear precipitating cause exists, and it is not reasonably possible that the event is caused by treatment with GC4419.

If the relationship between the AE/SAE and the investigational product is determined to be “possibly related” the event will be considered as related to the investigational product for the purposes of expedited regulatory reporting.

## **11.4. Recording Adverse Events**

All AEs must be recorded on the appropriate CRF regardless of the severity or relationship to GC4419. All AEs that meet the seriousness criteria should also be recorded on the SAE Report Form. All SAEs must be reported to the Sponsor or delegated organization within the timeline stated in [Section 11.2](#).

The recording of AEs will be based on data obtained from the following sources:

- Medical and surgical history
- Physical examinations including vital signs
- Clinical laboratory test results
- Subject verbal reports to the investigational staff and documented in the medical chart

All clinical events, including both observed (such as any reaction at sites of application) and volunteered problems, complaints, or symptoms, are to be recorded. The need to capture this information is not dependent upon whether the clinical event is associated with GC4419 use. AEs resulting from concurrent illnesses, reactions to concurrent medications or symptomatic progression of disease states are also to be recorded.

The information to be recorded for AEs will include:

- The specific type of event in standard medical terminology – diagnosis if known, is preferred over symptoms
- Duration of the clinical event (start and stop dates)
- Severity (Grade 1, 2, 3, 4, or 5) of the clinical event
- Seriousness (SAE) criteria, if applicable
- Relationship of the AE to GC4419, RT and chemotherapy as defined in [Section 11.3](#)
- Management of GC4419 administration and other action taken to alleviate the clinical events
- Clinical outcome of the AE

